5.4 BLINDING

This is an open-label study.

5.5 TREATMENT COMPLIANCE

All doses of the study drug will be administered in the clinical site under direct observation of site personnel and recorded in the eCRF. Clinic personnel will confirm that the subject has received the entire dose of study drug.

The date and time of study drug dosing will be recorded on the appropriate page in the eCRF. If a subject is not administered study drug, the reason for the missed dose will be recorded.

5.5.1 Prior and Concomitant Medications

Restrictions for prior and concomitant medications and therapies are provided in Section 4.1 and Section 4.2. Prior and concomitant medications and therapies will be coded using the latest version of the World Health Organization Drug Dictionary available at initiation of the study.

5.5.1.1 Prior Medications

Information regarding prior medications taken by the subject within the 30 days before signing the informed consent form (ICF) will be recorded in the subject's eCRF.

5.5.1.2 Concomitant Medications

Any concomitant medication deemed necessary for the welfare of the subject during the study may be given at the discretion of the investigator. If a concomitant medication is taken, a joint decision will be made by the investigator and the sponsor to continue or discontinue the subject based on the time the medication was administered, its pharmacology and PK, and whether the use of the medication will compromise the safety of the subject or the interpretation of the data. The investigator is responsible for ensuring that details regarding the medication are adequately recorded in the eCRF.

6. STUDY PROCEDURES

Before performing any study procedures, all potential subjects will sign an ICF as outlined in Section 9.2.2.3. Subjects will undergo study procedures at the time points specified in the schedule of events for Parts 1 and 2 (Section 3.1 and Section 3.2, respectively).

The total amount of blood collected from each subject over the duration of the study, including any extra assessments that may be required, will not exceed 500 mL.

6.1 PHARMACOKINETIC ASSESSMENTS AND ENDPOINTS

Single Dose (Part 1):

Blood samples for analysis of concentrations of aramchol and its metabolites in plasma will be collected at the following time points: before dosing (0 hour) and at 1, 2, 3, 4, 5, 6, 8, 10, 12, 14, 18, 24, 48, 72, 96, 120, 144, 168, 192, and 240 hours (the last 2 time points are for hepatically impaired subjects only) after administration of aramchol. Acceptable time deviations are ± 5 minutes for 0 to 4 hours, ± 10 minutes for >4 to 8 hours, ± 15 minutes for >8 to 24 hours, ± 30 minutes for >24 to 72 hours, and ± 60 minutes for >72 hours to 240 hours.

The following plasma PK parameters will be calculated as endpoints for aramchol using actual sampling times rather than scheduled sampling times:

- AUC from time 0 to the last quantifiable concentration (AUC_{0-t})

- AUC from time 0 extrapolated to infinity (AUC_{0-inf})
- Maximum observed plasma concentration (C_{max})
- Time to reach maximum observed plasma concentration (T_{max})
- Time to the first measurable plasma concentration (T_{lag})
- Apparent terminal elimination half-life ($t_{1/2}$)
- Apparent oral clearance (CL/F)
- Apparent volume of distribution (V_z/F)
- Elimination rate constant (k_e)

Multiple Dose (Part 2):

Blood samples for analysis of concentrations of aramchol and its metabolites in plasma will be collected before the AM dose on Days 1, 4, 8, 9, 10, 11, and 12 and at the following times after the AM dose on Day 12: 1, 2, 3, 4, 5, 6, 8, 10, and 12 hours. Acceptable time deviations are ± 5 minutes for 0 to 4 hours, ± 10 minutes for >4 to 8 hours, and ± 15 minutes for >8 to 12 hours.

The following plasma PK parameters on Day 12 will be calculated as endpoints for aramchol using actual sampling times rather than scheduled sampling times (if conducted):

- AUC from time 0 to the dosing interval tau at steady state ($AUC_{0-tau, ss}$)
- Maximum observed plasma concentration at steady state ($C_{max, ss}$)
- Time to reach maximum observed plasma concentration at steady state ($T_{max, ss}$)
- Minimum observed plasma concentration at steady state ($C_{min, ss}$)
- Time of minimum observed plasma concentration at steady state ($T_{min, ss}$)
- Average plasma concentration at steady state ($C_{avg, ss}$)

Time to reach steady state will also be estimated graphically by assessing trough plasma concentrations (ie, pre-AM dosing on Days 1, 4, 8, 9, 10, 11, and 12) over 12 days of administration.

6.1.1 Pharmacokinetic Sample Collection

Details for the collection, processing, storage, and shipping of PK samples will be provided to the clinical site separately.

6.1.2 Pharmacokinetic Sample Analysis

Pharmacokinetic samples will be analyzed using a validated liquid chromatography coupled with tandem mass spectrometry assay for aramchol in human plasma. Assay results and validation details will be provided in a separate bioanalytical report. Stored samples of plasma will also be analyzed for aramchol metabolites pending results of a mass balance study.

6.2 SAFETY ASSESSMENTS AND ENDPOINTS

Safety and tolerability will be assessed by the following endpoints: monitoring and recording of AEs, clinical laboratory test results (hematology, coagulation, serum chemistry, and urinalysis), vital sign measurements, 12-lead ECG results, and physical examination findings.

For all safety assessments, the investigator will determine whether results are clinically significant, which is defined as any variation in a result that has medical relevance and may result in an alteration in medical care (eg, active observation, diagnostic measures, or therapeutic measures). If clinical significance is noted, the result and reason for significance will be documented and an AE reported on the AE page in the subject's eCRF. The investigator will monitor the subject until the result has reached the reference range or the result at screening, or until the investigator determines that follow-up is no longer medically necessary.

6.2.1 Adverse Events

Adverse events will be assessed from the time the subject signs the ICF until EOS and should be followed until they are resolved, stable, or judged by the investigator to be not clinically significant.

The investigator is responsible for ensuring that all AEs and SAEs are recorded in the eCRF and SAEs are reported to the sponsor, regardless of their relationship to study drug or clinical significance. If there is any doubt as to whether a clinical observation is an AE, the event should be reported.

6.2.1.1 Adverse Event Definitions

An AE is defined as any untoward medical occurrence associated with the use of a drug in humans, whether or not considered drug related. Subjects will be instructed to contact the investigator at any time after signing the ICF if any symptoms develop.

A treatment-emergent AE is defined as any event not present before exposure to study drug or any event already present that worsens in intensity or frequency after exposure.

A suspected adverse reaction is any AE for which there is a reasonable possibility that the study drug caused the AE. For the purposes of investigational new drug safety reporting, “reasonable possibility” means that there is evidence to suggest a causal relationship between the study drug and the AE. A suspected adverse reaction implies a lesser degree of certainty about causality than an adverse reaction.

An adverse reaction is any AE caused by a study drug. Adverse reactions belong to a subset of all suspected adverse reactions and indicate that there are reasons to conclude that the study drug caused the event.

An AE or suspected adverse reaction is considered “unexpected” if it is not listed in the investigator’s brochure or if it occurs with specificity or severity that has not been previously observed with the study drug being tested.

An AE or suspected adverse reaction is considered an SAE/suspected unexpected serious adverse reaction if, in the view of either the investigator or sponsor, it results in any of the following outcomes:

- Death
- Life-threatening AE
- Inpatient hospitalization or prolongation of existing hospitalization
- Persistent or significant incapacity or substantial disruption of the ability to conduct normal life functions
- Congenital anomaly or birth defect

Important medical events that may not result in death, be life threatening, or require hospitalization may be considered serious when, based upon appropriate medical judgment, they may jeopardize the subject and may require medical or surgical intervention to prevent

one of the outcomes listed in this definition. Examples of such medical events include allergic bronchospasm requiring intensive treatment in an emergency room or at home, blood dyscrasias or convulsions that do not result in inpatient hospitalization, or the development of drug dependency or drug abuse.

An AE or suspected adverse reaction is considered “life threatening” if, in the view of either the investigator or sponsor, its occurrence places the subject at immediate risk of death. It does not include an AE or suspected adverse reaction that might have caused death if it had been more severe.

6.2.1.2 Eliciting and Documenting Adverse Events

Subjects will be asked a standard question to elicit any medically related changes in their well-being. They will also be asked if they have been hospitalized, had any accidents, used any new medications, or changed concomitant medication regimens (both prescription and over-the-counter medications).

In addition to subject observations, AEs will be documented from any data collected on the AE page in the eCRF (eg, laboratory values, physical examination findings, and ECG changes) or other documents that are relevant to subject safety.

6.2.1.3 Reporting Adverse Events

All AEs reported or observed during the study will be recorded in the source documentation and on the AE page in the eCRF. Information to be collected includes drug treatment, type of event, time of onset, dosage, investigator-specified assessment of severity and relationship to study drug, time of resolution of the event, seriousness, any required treatment or evaluations, and outcome. Any AEs resulting from concurrent illnesses, reactions to concurrent illnesses, reactions to concurrent medications, or progression of disease states must also be reported. All AEs will be followed until they are resolved, stable, or judged by the investigator to be not clinically significant. The Medical Dictionary of Regulatory Activities will be used to code all AEs.

Any medical condition that is present at the time that the subject is screened but does not deteriorate should not be reported as an AE but will be recorded as medical history. However, if it deteriorates at any time during the study, it should be recorded as an AE.

Any AE that is considered serious by the investigator or that meets SAE criteria (Section [6.2.1.1](#)) must be reported to the sponsor (or the sponsor’s designee) following the

guidelines provided on the study SAE form as soon as site personnel/investigator have become aware of the event and no later than 24 hours regardless of the relationship to the study drug. The investigator will assess whether there is a reasonable possibility that the study drug caused the SAE.

Serious AE report form completion and reporting must not be delayed even when information is incomplete at the time of the initial report. Any additional (follow-up) information that becomes available after the initial reporting should be forwarded in a follow-up SAE report form by the site personnel within 24 hours of the information becoming available.

All SAEs should be followed until resolution or stabilization of all parameters (including laboratory) return to baseline or until the investigator assesses them as stable or until the subject is lost to follow-up.

The sponsor will be responsible for notifying the relevant regulatory authorities of any SAE as outlined in US Title 21 Code of Federal Regulations (CFR) Parts 312 and 320. The investigator is responsible for notifying the institutional review board (IRB) directly.

For this study, the following contact information will be used for SAE reporting:

6.2.1.4 Assessment of Severity

The severity (or intensity) of an AE refers to the extent to which it affects the subject's daily activities and will be classified as mild, moderate, or severe using the following criteria:

- Mild: These events require minimal or no treatment and do not interfere with the subject's daily activities.
- Moderate: These events result in a low level of inconvenience or require minor therapeutic measures. Moderate events may cause some interference with normal functioning.
- Severe: These events interrupt a subject's usual daily activity and may require systemic drug therapy or other treatment. Severe events are usually incapacitating.

Changes in the severity of an AE should be documented to allow the duration of the event at each level of intensity to be assessed. An AE characterized as intermittent does not require documentation of the onset and duration of each episode.

6.2.1.5 Assessment of Causality

The investigator's assessment of an AE's relationship to study drug is part of the documentation process but is not a factor in determining what is or is not reported in the study.

The investigator will assess causality (ie, whether there is a reasonable possibility that the study drug caused the event) for all AEs and SAEs. The relationship will be classified as follows:

- Not related: There is not a reasonable possibility of relationship to study drug. The AE does not follow a reasonable temporal sequence from study drug administration or can be reasonably explained by the subject's clinical state or other factors (eg, disease under study, concurrent diseases, and concomitant medications).
- Related: There is a reasonable possibility of relationship to study drug. The AE follows a reasonable temporal sequence from study drug administration and cannot be reasonably explained by the subject's clinical state or other factors (eg, disease under study, concurrent diseases, or concomitant medications), represents a known reaction to the study drug or other drugs in its class, is consistent with the known pharmacological properties of the study drug, and/or resolves with discontinuation of the study drug (and/or recurs with rechallenge, if applicable).

6.2.1.6 Follow-up of Adverse Events

All AEs must be reported in detail on the appropriate page in the eCRF and followed until they are resolved, stable, or judged by the investigator to be not clinically significant.

6.2.2 Clinical Laboratory Testing

Clinical laboratory tests will be performed by the clinical sites' local laboratories. Blood and urine samples will be collected and prepared using standard procedures.

Repeat clinical laboratory tests may be performed at the discretion of the investigator, if necessary, to evaluate inclusion and exclusion criteria or clinical laboratory abnormalities. The clinical laboratory that will perform the tests will provide the reference ranges for all clinical laboratory parameters. Abnormal clinical laboratory values will be flagged as either high or low (or normal or abnormal) based on the reference ranges for each laboratory parameter.

Single Dose (Part 1):

Clinical laboratory testing will occur at screening; check-in; on Day 4; prior to discharge on Day 8 (healthy subjects) or Day 11 (hepatically impaired subjects); and at EOS.

Multiple Dose (Part 2):

Clinical laboratory testing will occur at screening; check-in; Days 4, 8, and 12; and at EOS.

The following clinical laboratory assessments will be performed for Parts 1 and 2:

Hematology	Absolute neutrophil count and differential, hematocrit, hemoglobin, mean corpuscular hemoglobin, mean corpuscular hemoglobin concentration, leukocyte count and differential (basophils, eosinophils, lymphocytes, monocytes, and neutrophils [absolute and differential]), mean corpuscular volume, platelet count, red blood cell count, and red blood cell distribution width
Coagulation	International normalized ratio, partial thromboplastin time, and prothrombin time
Serum chemistry	Alanine aminotransferase, albumin, alkaline phosphatase, aspartate aminotransferase, bilirubin (total), blood urea nitrogen, calcium, carbon dioxide, chloride, cholesterol (total, high-density lipoprotein, and calculated low-density lipoprotein), creatinine, gamma-glutamyltransferase, globulin, glucose, lactate dehydrogenase, phosphorus, potassium, sodium, total protein, triglycerides, and uric acid
Urinalysis	Bilirubin, color, glucose, ketones, leukocyte esterase, reflex microscopy (performed if dipstick is positive for protein or the blood value is 1+ or greater; and includes bacteria, casts, crystals, epithelial cells, red blood cells, and white blood cells), nitrites, occult blood, pH, protein, specific gravity, turbidity, and urobilinogen
Serology	Hepatitis B surface antigen, hepatitis C virus antibody, and human immunodeficiency virus antibody types 1 and 2 (screening only)
Other analyses	All subjects: Urine drug screen (alcohol, amphetamines, barbiturates, benzodiazepines, cannabinoids, cocaine metabolites, methamphetamines, methylenedioxymethamphetamine, and opiates [including heroin, codeine, and oxycodone]) Female subjects: Follicle-stimulating hormone (postmenopausal women; screening only), urine pregnancy test (human chorionic gonadotropin) (screening, check-in, and EOS [or early termination])

6.2.3 Vital Sign Measurements

All vital signs will be measured after the subject has been in the seated position for at least 5 minutes. Vital signs will include systolic and diastolic blood pressure, pulse rate, respiratory rate, and body temperature.

Single Dose (Part 1):

Vital signs will be measured at screening and check-in; prior to aramchol dosing; 4, 12, and 24 hours after dosing; Days 3 and 4; prior to discharge on Day 8 (healthy subjects) or Day 11 (hepatically impaired subjects); and at EOS.

Multiple Dose (Part 2):

Vital signs will be measured at screening and check-in, prior to the AM aramchol dosing on Day 1; 4 hours after the AM dose on Days 1 through 12; prior to discharge on Day 13; and at EOS.

6.2.4 Electrocardiograms

All ECGs will be measured after the subject has been in the supine position for at least 5 minutes. A single repeat measurement is permitted at screening for eligibility determination.

Electrocardiogram assessments will include comments on whether the tracings are normal or abnormal, rhythm, presence of arrhythmia or conduction defects, morphology, any evidence of myocardial infarction, or ST-segment, T-wave, and U-wave abnormalities. In addition, measurements of the following intervals will be measured and reported: RR interval, PR interval, QRS width, QT interval, and QTcF.

Single Dose (Part 1):

Single 12-lead ECG recordings will be made at screening and check-in; at 6, 12, and 24 hours after dosing; on Day 4; prior to discharge on Day 8 (healthy subjects) or Day 11 (hepatically impaired subjects); and at EOS.

Multiple Dose (Part 2):

Single 12-lead ECG recordings will be made at screening and check-in; on Days 4, 8, and 12; and at EOS.

6.2.5 Physical Examinations

Subjects will undergo a physical examination at the time points specified in the schedule of events for Parts 1 and 2 (Section 3.1 and Section 3.2, respectively). A full physical examination will include, at minimum, assessment of skin, head, ears, eyes, nose, throat, neck, thyroid, lungs, heart, cardiovascular system, abdomen, lymph nodes, and musculoskeletal system/extremities. A brief physical examination will include, at minimum, assessment of skin, lungs, cardiovascular system, and abdomen (liver and spleen). Interim physical examinations may be performed at the discretion of the investigator, if necessary, to evaluate AEs or clinical laboratory abnormalities.

Height and weight will be measured, and BMI will be calculated at screening only. Only weight will be measured at check-in and EOS (or early termination).

7. STATISTICAL ANALYSIS PLANS

7.1 SAMPLE SIZE CALCULATIONS

For Part 1, up to 48 subjects are planned: 8 subjects each in the mild (Cohort A), moderate (Cohort B), and severe (Cohort C) hepatic impairment cohorts and 8 to 24 healthy control subjects with normal hepatic function (Cohort D). For Part 2, at least 8 subjects with mild and moderate or moderate and severe hepatic impairment and up to 8 healthy control subjects with normal hepatic function are planned. The sample size was chosen for this study based on clinical and practical considerations and not on a formal statistical power calculation. The US Food and Drug Administration Guidance for Industry, Pharmacokinetics in Patients With Impaired Hepatic Function: Study Design, Data Analysis, and Impact on Dosing and Labeling (DHHS 2003) was used as a guide to select the sample size, which is considered sufficient to adequately assess the safety and PK profiles of aramchol.

In the event of early withdrawals or discontinuations, subjects may be replaced at the discretion of the investigator, and after consultation with the medical monitor and sponsor if the number of completers will be less than 6 subjects in any cohort.

7.2 ANALYSIS SETS

The analysis populations are as follows:

- The PK population will include subjects who receive at least 1 dose of aramchol and have sufficient concentration data to support accurate estimation of at least 1 PK parameter. In

Part 1, subjects who experience vomiting within 6 hours after study drug dosing will be excluded from the PK analysis.

- The safety population will include all subjects who receive at least 1 dose of aramchol.

7.3 STATISTICAL ANALYSIS

Details of all statistical analyses will be described in a statistical analysis plan. All data collected will be presented in data listings. Data from subjects excluded from an analysis population will be presented in the data listings but not included in the calculation of summary statistics.

For categorical variables, frequencies and percentages will be presented. Continuous variables will be summarized using descriptive statistics (number of subjects, mean, standard deviation [SD], minimum, median, and maximum).

Baseline demographic and background variables will be summarized by hepatic condition for all subjects. The number of subjects who enroll in the study and the number and percentage of subjects who complete the study will be presented. Frequency and percentage of subjects who withdraw or discontinue from the study, and the reason for withdrawal or discontinuation, will also be summarized.

7.3.1 Pharmacokinetic Analyses

Plasma concentrations will be listed and summarized descriptively (number of subjects, arithmetic mean, SD, coefficient of variation [CV], minimum, median, and maximum). Plasma concentration versus actual time profiles for each subject will be presented graphically. The mean plasma concentration versus scheduled time profiles will be presented graphically.

Pharmacokinetic parameters derived from plasma concentration data using noncompartmental methods with Phoenix[®] WinNonlin[®] (Certara USA Inc, Princeton, New Jersey) Version 8.0 or higher will be summarized by hepatic group using descriptive statistics (number of subjects, arithmetic mean, SD, CV, minimum, median, and maximum). Geometric mean and geometric CV will also be calculated for AUCs and C_{max} . The AUC_{0-t} , AUC_{0-inf} , and C_{max} values may also be expressed in terms of unbound drug concentrations.

An analysis of variance (ANOVA) model will be performed on the natural logarithms of AUC_{0-t} , AUC_{0-inf} , and C_{max} to calculate the ratio of geometric means and its 90% confidence interval between subjects with hepatic impairment and the corresponding healthy control

subjects, as appropriate. The ANOVA model will include hepatic group (normal matching mild, mild, normal matching moderate, moderate, normal matching severe, and severe, where applicable) as a fixed effect.

For AUC_{0-t} , AUC_{0-inf} , and C_{max} , a linear regression model will be performed on the natural logarithms of AUC_{0-t} , AUC_{0-inf} , and C_{max} as dependent variables and each of the following natural-log-transformed hepatic function estimates as independent variables: Child-Pugh classification score (in subjects with hepatic impairment only), baseline serum bilirubin, serum albumin, and prothrombin time. The regression coefficients representing the relationship between the PK parameters and the hepatic function estimates will be estimated together with their 90% confidence intervals from the regression model.

Sensitivity analyses may be conducted to investigate the potential impact of imbalance existing across hepatic impairment groups in the distribution of the baseline covariates used in subject matching (eg, body weight) and, if data suggest, appreciable differences in PK exposure (AUC_{0-t} , AUC_{0-inf} , and C_{max}) across different values of the same baseline covariate.

Detailed descriptions of the analyses in this study will be presented in the statistical analysis plan.

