5.3 METHOD OF ASSIGNING SUBJECTS TO TREATMENT GROUPS

This is a nonrandomized study. At screening, hepatically impaired subjects will be assigned to a study group based on their level of hepatic function according to the Child-Pugh classification system, as shown in Table 5–1. To allocate subjects to the appropriate cohort of hepatic impairment severity, a history of higher severity that has responded to medication will be taken into account. Thus, subjects with a history of Grade 3 or 4 encephalopathy that have responded to treatment with medicines such as lactulose or neomycin may be included with the subject receiving the point score for Grade 3 or 4 encephalopathy. Similarly, subjects with a history of moderate or severe ascites that have responded to diuretics may be included with the subject receiving the higher score.

Table 5–1 Child-Pugh Classification System

Points ^(a)	Bilirubin (mg/dL)	Albumin (g/dL)	Prothrombin Time (seconds prolonged)	Encephalopathy (grade) ^(b)	Ascites (grade)
1	<2.0	>3.5	<4	None (Grade 0)	Absent
2	2.0 to 3.0	2.8 to 3.5	4 to 6	1 or 2	Slight
3	>3.0	<2.8	>6	3 or 4 or subjects receiving medication(s) to prevent encephalopathy	Moderate or severe subjects on medication(s) to control ascites

Abbreviation: INR, international normalized ratio.

^(a) For each category (bilirubin, albumin, prothrombin time or INR, encephalopathy grade, and ascites), points are assigned based on the subject’s condition and the criterion met. The Child-Pugh class is assigned based on the sum of these points as follows: Child-Pugh Class A or mild hepatic impairment if the sum is 5 or 6 points; Child-Pugh Class B or moderate hepatic impairment if the sum is 7 to 9 points; and Child-Pugh Class C or severe hepatic impairment if the sum is 10 to 15 points.

^(b) Grade 0: normal consciousness, personality, neurological examination, electroencephalogram.
 Grade 1: restless, sleep disturbed, irritable/agitated, tremor, impaired handwriting, 5 count-per-second waves.
 Grade 2: lethargic, time-disoriented, inappropriate, asterixis, ataxia, slow triphasic waves.
 Grade 3: somnolent, stuporous, place-disoriented, hyperactive reflexes, rigidity, slower waves.
 Grade 4: unarousable coma, no personality/behavior, decerebrate, slow 2-3 count-per-second delta activity.

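### The exposure regression uses log prothrombin time pooled over three local laboratories with no normalisation; the slope can be biased in either direction, and INR from the same panel is the better predictor

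*Combined protocol and SAP*

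**What the plan says.** Section 7.3.1 (same text in the synopsis) takes the natural logs of AUC0-t, AUC0-inf and Cmax as dependent variables and "each of the following natural-log-transformed hepatic function estimates as independent variables". These are the "Child-Pugh classification score (in subjects with hepatic impairment only") and "baseline serum bilirubin, serum albumin, and prothrombin time". The restriction to impaired subjects is attached to the Child-Pugh score alone, so the PT model as written includes the healthy controls. The coefficients are to be reported "together with their 90% confidence intervals from the regression model". No unit for PT, no normalisation and no site or laboratory term is stated.

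Section 6.2.2: "Clinical laboratory tests will be performed by the clinical sites' local laboratories", and "The clinical laboratory that will perform the tests will provide the reference ranges for all clinical laboratory parameters". The only use stated for those ranges is flagging abnormal values. The coagulation panel in the same section is "International normalized ratio, partial thromboplastin time, and prothrombin time", so INR is collected as an item separate from PT. Section 4 plans three US centres.

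For cohort assignment, Table 5-1 in Section 5.3 heads its column "Prothrombin Time (seconds prolonged"), and its footnote (a) accepts either PT or INR for that component.

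**The concern.** PT in seconds depends on the laboratory's reagent and instrument. On the log scale a difference in normal PT is a constant shift for everyone tested at that site, and a difference in reagent sensitivity stretches or compresses the scale. A model with ln PT alone removes neither.

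If cohorts are spread evenly over sites, the shift acts as measurement error in the covariate and pulls the slope towards zero. If one site supplies most of the controls or most of the severe subjects, the shift is confounded with hepatic function and the bias can go either way. Such a link is possible: cohorts open in sequence (Section 3), impaired subjects enrol as they become eligible (Section 5.3), and no balancing by site is planned. The slope and its interval are the only outputs stated for this regression.

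**Working it through.** **Plan's own figure.** The plan states no slope, PT variance, power or laboratory spread, so there is nothing to reproduce. The Part 1 maximum does check: 3 × 8 + 24 = 48 subjects.

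**Which PT scale is meant.** INR is listed separately, so it is not the obvious reading of PT. Seconds prolonged cannot be meant, because its log is undefined for a control with zero or negative prolongation. That leaves seconds, as an inference.

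**Relation between the scales.** With MNPT the laboratory's mean normal PT and ISI its reagent's international sensitivity index, ln INR = ISI × (ln PT − ln MNPT). MNPT is therefore an additive site shift in ln PT and ISI a site-specific scale factor.

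**Attenuation, cohorts balanced over sites.** Factor = var(true ln PT) / [var(true ln PT) + var(laboratory shift)]. Both SDs are assumptions.

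| True SD of ln PT | Lab SD 0.03 | 0.05 | 0.08 | 0.10 |
|---|---|---|---|---|
| 0.10 | 0.92 | 0.80 | 0.61 | 0.50 |
| 0.15 | 0.96 | 0.90 | 0.78 | 0.69 |
| 0.20 | 0.98 | 0.94 | 0.86 | 0.80 |
| 0.25 | 0.99 | 0.96 | 0.91 | 0.86 |

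Smallest loss: 0.0625 / (0.0625 + 0.0009) = 0.986, about 1%. Largest: 0.01 / (0.01 + 0.01) = 0.50.

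**Simulation.** Assumptions: 24 controls and 8 subjects each with mild, moderate and severe impairment; mean ln INR 0, 0.10, 0.25 and 0.45; within-group SD 0.07; residual SD 0.4; true slope 1.0 per unit of ln INR; ISI 1; 4000 runs. In the linked settings 80% of controls attend one site, while 80% to 90% of each impaired cohort is split between the other two. Mean slope on ln PT:

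| Normal PT at the three sites (s) | Balanced | Most controls at lowest-PT site | Most controls at highest-PT site |
|---|---|---|---|
| 12 / 12 / 12 | 0.99 | 0.99 | 1.01 |
| 11.5 / 12 / 12.5 | 0.97 | 0.89 | 1.07 |
| 11 / 12 / 13 | 0.88 | 0.78 | 1.05 |
| 10.5 / 12 / 13.5 | 0.76 | 0.68 | 0.94 |

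The balanced column agrees with the formula. The assumed group means give a between-group variance of 8 × (0.0100 + 0.0625 + 0.2025)/48 − (8 × 0.80/48)² = 0.0458 − 0.0178 = 0.0281 (unrounded difference). Adding 0.07² = 0.0049 gives 0.0330. For 11 / 12 / 13 s the laboratory SD is 0.068, and 0.0330 / (0.0330 + 0.0046) = 0.88.

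**Reagent sensitivity.** With equal normal PT and ISI 1.0 / 1.2 / 1.4, the mean slope on ln PT is 1.16. Part of this is a change of unit: an ISI of 1.2 at every site would give exactly 1.2. The result therefore shows mainly that the ln PT slope depends on which reagents the sites happen to use. With equal normal PT, the ratio to local control differs from PT only by a constant in logs, so its slope is also 1.16. Adding a site term gives 1.17.

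**Slope on ln INR.** 0.99 to 1.01 in every setting. The simulation treats INR as free of laboratory error, so this is the best case.

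**Interval coverage.** With slope 1.5, residual SD 0.47, 48 subjects and balanced sites, coverage of the nominal 90% interval at laboratory SDs of 4%, 6%, 8% and 10% is about 89%, 87%, 81% and 73% when the true SD of ln PT is 0.125. When it is 0.14, coverage is about 89%, 87%, 82% and 75%.

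**The case against.** **The harm is not shown.** The documents give no reagent, ISI, normal PT or site mix by cohort. A reader might infer that the slope will be diluted; they do not support that. If the laboratories agree there is no bias, and inflation is as open as attenuation. This objection stands and sets the wording.

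**Seconds is an inference.** Section 7.3.1 gives no unit, and footnote (a) to Table 5-1 accepts PT or INR. Nor does the table say why it scores prolongation, so it is no evidence that the authors had reagent differences in mind. This stands, although seconds remains the natural reading.

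**No single attenuation figure can be given.** At a laboratory SD of 0.08 the factor runs from 0.61 to 0.91, depending on a spread of ln PT that is not stated. The coverage and simulation figures also use the maximum of 48 subjects, although Cohort A is conditional and controls may number only 8. At the low end the interval barely suffers: its half-width is about half the slope, and coverage at a 4% laboratory SD is about 89%. This stands.

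**Detail is deferred.** Sections 7.3 and 7.3.1 send details to a separate statistical analysis plan that is not part of the text reviewed and might settle the scale. This weakens the point only in part, because Section 7.3.1 already names the predictor.

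**The reach is small.** A reader might infer that the primary comparison is compromised. It is not: the primary objective is served by the ANOVA on hepatic group, which does not use PT. No stated decision depends on this slope; Cohort A opens on CL/F, and Part 2 dosing looks to clearance in Part 1. This stands in full.

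**Conclusion.** The point holds in a conditional form. The plan pools ln PT, most naturally in seconds, over three sites' local laboratories with nothing to put them on one scale, while a normalised measure sits unused in the same panel. Under the assumed laboratory SDs of 3% to 10% and true ln PT SDs of 0.10 to 0.25, balanced cohorts give attenuation of about 1% to 50%. With site and cohort linked, the simulated slopes run from 0.68 to 1.07 against a true 1.0. Differing ISI gave 1.16 relative to the slope per unit of ln INR. The true figure could be zero. The affected result is one of four predictors in a supportive regression, so this is a worthwhile low-cost correction and not a threat to the study's main conclusion.

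**What to change.** In the synopsis and Section 7.3.1, name ln INR as the coagulation predictor in place of ln PT. Keep ln PT as a sensitivity analysis, or the log of PT over the local control value where that value is captured. Fix this order before exposure data are seen, so that the choice between PT and INR is not made afterwards.

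INR should come first for three reasons: it is already collected, its log is defined for controls, and it adjusts for both normal PT and ISI. The ratio to control and a site term each leave ISI differences in place. The control PT is also not listed in Section 6.2.2, and since Table 5-1 may be scored from INR, its capture is not assured.

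The cost is a wording change in two places, with no new sample or assay. The downside is that INR does not remove every laboratory difference in liver disease, which is a reason to keep the sensitivity analysis.
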